A proposed randomized clinical trial of the effectiveness of a new breastfeeding- supportive texting program designed specifically for African-American/Black expectant women, as compared to a national maternal health texting program, on rates of exclusive breastfeeding at 2months; Short title: TOPS – Texting to Promote Breastfeeding).

XXXXXXXXXXXXXX

NCT06375655

01/19/2024

Objectives

Specific Aims

- 1. Demonstrate the feasibility and acceptability of a scaled-up program to deliver Team2BF text messages to AA/B expectant women considering breastfeeding.
- 2. Compare breastfeeding outcomes in the group receiving Team2BF with rates among those receiving Bright By Text.
- 3. Compare breastfeeding related knowledge and self-efficacy and social support as moderators of the relationship between the texting intervention and breastfeeding outcomes. (Exploratory aim)
- 4. Compare other key health outcomes (appointment attendance and vaccine receipt and book reading to infant) between the groups to verify that a focus on breastfeeding enhances rather than detracts from general maternal-infant health outcomes. (Exploratory aim)

Study Hypotheses

- Participants will find the Team2BF intervention acceptable as measured by >90%
 continuation, by >75% top score helpfulness of messages for breastfeeding and >75%
 endorsement of friend and family referral.
- 2. Participants receiving Team2BF will have significantly higher exclusive breastfeeding rates at 2 months as compared to participants receiving Bright By Text.
- 3. Breastfeeding knowledge, perceived social support for exclusive breastfeeding and self-efficacy will positively moderate the relationship between texting and breastfeeding outcomes, with those in the Team2BF group demonstrating a significantly greater increase in these domains with time as compared to the Bright By Text group.
- 4. Participants in both groups will have >75% rates of attendance among mothers at the (2-6 weeks) postpartum obstetrical visit and >75% rates of attendance and vaccine receipt for infants at the 2 month (6-12 weeks) well care visit.

Background

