For those who do not respond to the surveys, we will send one automated reminder text, and call up to 3 times, to make sure there are not technical difficulties. For those who STOP ALL or STOP SO MANY (to receive only one message per time point (by week prenatally or by day postpartum), we will ask, "Why unsubscribe?" If the participant does not respond, or does not respond to any of the surveys, we will call or email (two tries only) to understand why.

Mothers can continue to receive monthly messages for months 6-12 postpartum for TEAM2BF and up to 8 years postpartum for Bright By Text but this will not be incentivized.

Mothers will be asked to enter their delivery date; as a backup plan we are requesting to check both Delivery Logs (the PI receives these daily weekdays – they include all UHCMC MacDonald Women's deliveries) and the maternal EMR (electronic medical record) to make sure we do not miss this date if a mother forgets to enter her delivery date, since a different set of text messages is delivered postpartum and the postpartum surveys begin.

- 2- Research participants' safety and comfort will be protected by their ability to text "STOP" to end all messaging. Additionally in the informed consent we will have contact information for the study team, and the participant can call or email the study team with any concerns or questions.
- 3- Participants will use their own smartphones for the study. The smartphone is a device but it is not being studied. The text messages are being studied. Given the definition of software as a medical device (The term "Software as a Medical Device" (SaMD) is defined as software intended to be used for one or more medical purposes that perform these purposes without being part of a hardware medical device. Reference-https://www.fda.gov/medical-devices/digitalhealth-center-excellence/software-medical-

- device-samd), the text messaging does not appear to be SaMD because it is not being used to treat, diagnose or manage a condition or disease.
- 4- The source records for the study will be the survey data that participants provide and the electronic medical record.

Study Timeline

| Time point | Surveys | Approximate Time Needed | | | |
|-----------------|---|-------------------------|--|--|--|
| | | | | | |
| Enrollment | Demographics (your name, age, family | 7-10 minutes | | | |
| | supports, WIC status, other basic info) | | | | |
| | Infant Feeding Intentions Survey (4 | | | | |
| | questions) | | | | |

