| | Breastfeeding Knowledge Quiz (4 | | | | |
| | questions – answers follow) | | | | |
| | Breastfeeding Self-Efficacy Scale (14 | | | | |
| | items) | | | | |
| One week after | Infant Feeding Information-what milk is | 2 minutes | | | |
| delivery (PP) | baby drinking? | | | | |
| One month PP | Infant Feeding Information | 2 minutes | | | |
| Two months PP | Infant Feeding Information | 15 minutes | | | |
| | Breastfeeding Knowledge Quiz | | | | |
| | Breastfeeding Self-Efficacy Scale | | | | |
| | Breastfeeding Social Support Scale (16 | | | | |
| | items) | | | | |
| | Maternal Satisfaction (6 questions) | | | | |
| Three months PP | Infant Feeding Information | 3-4 minutes | | | |
| | Healthy Development (1 question) | | | | |
| | Maternal Satisfaction (6 questions) | | | | |
| Six months PP | Infant Feeding Information | 8-17 minutes | | | |
| | Healthy Development | | | | |
| | Maternal Satisfaction (6 questions) | | | | |
| | Study Thank you Survey | | | | |

Data to be Collected for your study

Outcome Measures

Aim #1 - Acceptability

Receipt of messages measures acceptability because participants can easily end messaging; if at least 90% of Team2BF participants continue receipt this will indicate acceptability of the intervention. This outcome will be enhanced by asking (a) a single 4 point Likert-scaled question

about the helpfulness of the texts for breastfeeding and (b) whether the participant would or would not refer a friend or family member to Team2BF.

Aim #2 – Breastfeeding Outcomes

The main outcome will be exclusive breastfeeding at 2 months because this is a meaningful milestone toward the public health goal of 6 months exclusive breastfeeding. We will assess partial and exclusive breastfeeding at hospital discharge and at 1, 2, 3 and 6 months post delivery using the World Health Organization definitions for exclusive and partial breastfeeding. We will also assess timing of discontinuation of breastfeeding if this occurs.

Aim #3 – Moderators of Breastfeeding Outcomes (Exploratory aim)

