To calculate sample size both current and near past breastfeeding rates are relevant. At the Rainbow Pediatric Practice (RPP, IRB # 11-16-07, using a 3 month annual snapshot) data from 2016-2020 inclusive years for full term and late preterm infants not admitted to Neonatal Intensive Care Unit who have an appointment in RPP in first month of life: 89/808 infants (11%) were exclusively breastfed at 2 months. Women Infants and Children Supplemental Feeding Program (WIC) Cuyahoga County data aligns with this estimate, showing "Fully Breastfed Infants" (defined as infants of participating breastfeeding women do not receive formula from the WIC Program) for the fiscal year 2021 with 594/5188 infants (11.4%) fully breasted. An increase from 11% to 14% would be clinically meaningful, and to achieve this with 80% power, alpha 0.05 (SD of not more than 5%) we need 36 mother-infant dyads per group, which is 72; and allowing for 10% attrition we aim to enroll 40 mothers per group (80 total).

Without published data on breastfeeding from Bright By Text participants, a 5% point difference between the two arms in this outcome can be considered clinically meaningful. The timing of breastfeeding cessation is the inverse of partial or exclusive breastfeeding and will be compared between the two arms at end of study (6 months); a 1 month difference between the groups can be considered clinically meaningful.

Risks to Research Participants

There is a risk of breach of confidentiality due to ongoing text messaging but this will be protected against by careful management of the texting system by study team members and by protecting and securing the data received. There is a risk of emotional distress if a participant's anxiety about breastfeeding is increased by receiving messages about breastfeeding from either texting program – this will be mitigated by providing resources through the messages, by the ability to unsubscribe promptly, and in the informed consent by emphasizing that this is a research study and breastfeeding help can be obtained from her health providers or the Ohio Breastfeeding Hotline. There is a risk of data overage or charge depending on what plan a participant is on – we cannot mitigate this, but all participants can unsubscribe whenever they choose. All participants can text STOP to unsubscribe at any point with either study arm and withdraw themselves from the research.

Provisions to Protect the Privacy Interests of Research Participants

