The privacy of participants will be protected. The consent process will occur in a private space or virtually where the potential participant can protect their own privacy. All interventions occur virtually on a personal phone, so participants are not exposed to others.

Potential Benefit to Research Participants

There are no direct benefits guaranteed to participants. Participants may benefit if the TEAM2BF messaging helps them with their breastfeeding and may benefit if Bright By Text

increases their wellness, but this cannot be guaranteed. We hope the information gained will help future women, their families and their health providers with breastfeeding and ultimately reduce racial inequities in breastfeeding.

Withdrawal of Research Participants

All participants can text STOP to unsubscribe at any point and withdraw themselves from the research and from each of the texting programs. A participant would be withdrawn is if there is any abuse of the texting system with receipt of inappropriate or profane messages. Mother participants who deliver prior to 36 weeks (35 and 6/7 weeks or before) will be exited from the study since the postnatal messaging is not tuned for prematurity.

Alternatives to Participation

The alternative to participation is simply not to participate. The research is not a substitute for clinical care.

Costs to Research Participants

There could be a cost for the texting for participants depending on their phone plan. The study team cannot be responsible for these costs.

Research Participant Compensation

At enrollment, at 1 week postpartum and at 1, 2, 3 and 6 months we will give \$25 gift card and a tangible gift (diapers+wipes or onesies).

Provisions to Monitor the Data to Ensure the Safety of Research Participants

The PI and research coordinator will meet at least every other week to review for adherence to protocol, trouble shooting, and any events. We will not convene a DSMB.

Drugs or Devices

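### The 90% continuation rule assumes that ending the texts is free, but the plan does not settle whether STOP also means leaving the study and its payments

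*Combined protocol and SAP*

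**What the plan says.** All references are to the combined protocol and SAP.

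- **Acceptability rule.** Outcome Measures, Aim #1, gives the rationale: "Receipt of messages measures acceptability because participants can easily end messaging". The mark it then sets is worded as follows: "if at least 90% of Team2BF participants continue receipt this will indicate acceptability of the intervention". A helpfulness item and a referral item supplement this. Study Hypotheses, item 1, asks for more than 90% continuation, and for more than 75% on each of the other two measures.
- **STOP as the end of messages.** Study Procedures, item 1, gives Team2BF mothers STOP ALL or STOP SO MANY (cut to one message per time point) and Bright By Text mothers STOP. Anyone who unsubscribes is invited to an interview, and the plan is to ask why she did so. Item 2 presents STOP as a way to end messaging. Neither item mentions leaving the study.
- **STOP as withdrawal.** The Risks section has this sentence: "All participants can text STOP to unsubscribe at any point with either study arm and withdraw themselves from the research". The section on withdrawal has a close parallel: "All participants can text STOP to unsubscribe at any point and withdraw themselves from the research and from each of the texting programs".
- **Payment.** The compensation section sets the time points as follows: "At enrollment, at 1 week postpartum and at 1, 2, 3 and 6 months we will give". What is handed over each time is a gift card worth $25 plus a gift in kind. For messages after month 6, Study Procedures says that mothers may continue "up to 8 years postpartum for Bright By Text but this will not be incentivized".
- **Use of the texts.** Study Procedures, item 1, says that reading and link clicks cannot be collected in the Team2BF system.

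**The concern.** Staying subscribed shows that a mother finds the texts acceptable only if leaving costs her nothing. The plan relies on that when it calls messaging easy to end. If STOP also takes her out of the research, it may take her out of the paid surveys too. A mother who dislikes the texts would then have a reason to ignore or mute them rather than stop, and she would still count as continuing. With no reading or click data, nothing in the Team2BF system would reveal this.

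At stake is the continuation part of Aim 1, which has its own numerical mark and is meant to inform a scaled-up programme. There is a second consequence. The Risks section offers unsubscribing as a protection against distress and data charges, and that protection is weaker if using it means leaving the study.

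**Working it through.** **1. What could be forgone.** The compensation schedule has six time points: enrollment, 1 week, and 1, 2, 3 and 6 months. The enrollment payment has already been received, so 6 - 1 = 5 remain for a mother who stops before the 1-week payment. That is 5 x $25 = $125 of a total 6 x $25 = $150, plus five gifts. A later stop puts less at stake.

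**2. What the rule requires.** The Data Analysis Plan aims for 40 mothers per group. At least 90% (Outcome Measures) is 0.90 x 40 = 36. More than 90% (Study Hypotheses) is 37.

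**3. Does STOP end payment?** Set side by side, the passages do not settle it.

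| Section | What STOP does | Surveys and payment afterwards |
|---|---|---|
| Study Procedures, items 1 and 2 | ends or reduces messages | not stated |
| Risks | unsubscribe and withdraw from the research | not stated |
| Withdrawal | same, and from the texting programs | not stated |
| Compensation | not mentioned | paid by time point; no condition given |

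The remark that receipt after month 6 is not incentivized suggests that receipt before then is. It does not say that payment depends on it.

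**4. How sensitive the rule would be.** The documents give no continuation rate in the absence of payment, so the rates below are assumptions. Let p be the proportion who would continue with no payment at stake, and s the share of would-be stoppers who stay for payment. Observed continuation is then q = p + (1 - p)s. For example, p = 0.80 and s = 0.50 give q = 0.80 + 0.20 x 0.50 = 0.90. The chance of meeting the rule is the binomial tail P(X >= 36), or P(X >= 37), with n = 40 and probability q.

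| p | s | q | P(at least 36 of 40) | P(at least 37 of 40) |
|---|---|---|---|---|
| 0.75 | 0 | 0.750 | 0.016 | 0.005 |
| 0.75 | 0.25 | 0.8125 | 0.107 | 0.043 |
| 0.75 | 0.50 | 0.875 | 0.429 | 0.246 |
| 0.75 | 0.75 | 0.9375 | 0.898 | 0.761 |
| 0.80 | 0 | 0.800 | 0.076 | 0.028 |
| 0.80 | 0.25 | 0.850 | 0.263 | 0.130 |
| 0.80 | 0.50 | 0.900 | 0.629 | 0.423 |
| 0.80 | 0.75 | 0.950 | 0.952 | 0.862 |
| 0.85 | 0 | 0.850 | 0.263 | 0.130 |
| 0.85 | 0.25 | 0.8875 | 0.526 | 0.327 |
| 0.85 | 0.50 | 0.925 | 0.822 | 0.647 |
| 0.85 | 0.75 | 0.9625 | 0.984 | 0.938 |

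In counts, 34 of 40 is 85.0% and fails under either wording, while 37 of 40 is 92.5% and passes under either. Three mothers separate the two results. The table shows that the rule would respond to a payment effect if there were one. It does not show that there is one.

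**The case against.** The strongest reply is that payment is for surveys, not for texts. The paid time points match the survey schedule in Study Timeline. Additional Information says that research surveys go from REDCap to all participants, including the arm whose texts come from an outside provider, so surveys and intervention texts can be separated. Mothers who unsubscribe are still to be contacted. The Risks and Withdrawal sentences can also be read as naming two rights rather than one act. On that reading, stopping costs nothing and the payment problem largely disappears.

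Much of this stands. A reader might infer that the plan makes mothers forfeit payment by texting STOP, and that continuation therefore will be inflated or is partly a measure of payment. The documents do not support that: forfeiture is an inference from the withdrawal wording. Nor can one say that mothers are told so, because the consent text is not available for review.

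It is also fair to say that continuation is one of three criteria. A mother who ignores texts she dislikes would be expected to score helpfulness and referral lower. STOP SO MANY gives her a middle course that no passage links to withdrawal. These points limit the consequence but do not remove it, because continuation keeps its own 90% mark. If helpfulness and referral are collected by the postpartum surveys, mothers withdrawn after STOP would also be missing from them.

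What the reply does not do is reconcile the passages. The plan nowhere says that a mother who stops the texts stays in follow-up and is still paid.

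**Conclusion.** The point holds as a conditional one. The plan justifies its continuation rule by the ease of stopping, and elsewhere describes STOP in terms that could make stopping costly. If STOP means withdrawal, up to $125 and five gifts could be at stake, and continuation could be raised by payment with no reading data to show it. If STOP ends messages only and payments go on, little of the problem remains.

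The payment count is exact. The probabilities rest on assumed values of p and s and on 40 mothers in the Team2BF arm; the documents support no estimate of the effect.

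A reader might also infer that the unpaid months 6 to 12 would isolate the effect of payment. They would not. Team2BF messages are then monthly, against weekly before delivery and daily for the first two weeks after it, and only mothers who have not already stopped remain. Aim #1 also gives no time window for the 90% rule, so the documents do not show that those months are excluded from it.

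**What to change.** 1. Reconcile Study Procedures, Risks and Withdrawal so that STOP, STOP ALL and STOP SO MANY end or reduce messages only. Make withdrawal from the research a separate, explicit request.
2. State in the protocol and the consent form that surveys, follow-up, payments and gifts do not depend on staying subscribed.
3. State whether a mother on STOP SO MANY counts as continuing, and choose between at least 90% and more than 90%; with 40 mothers these differ by one.
4. Continuation in months 6 to 12 may be reported descriptively, but not as a measure of the payment effect.

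The cost is protocol and consent wording, a few gift cards and gifts for mothers who stop the texts, and a continuation figure that may be lower. Since Team2BF texts and research surveys both go through REDCap, the team should check that a STOP command does not also block survey invitations.

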Exclusive breastfeeding at 6 months is recommended by professional bodies worldwide, with profound health benefits for mothers, infants and society, yet achievement continues to be an elusive goal with profound national racial inequities persisting. [1-5] Nationally 83.9% of all mothers but just 75.5% of African American/Black (AA/B) mothers initiate breastfeeding; with respect to the HealthyPeople 2030 goal for 6 months exclusive breastfeeding of 42.4%, 24.9% of all mothers but just 19.8% of AA/B mothers are achieving this goal. [6,7] The state of Ohio faces similar racial breastfeeding inequities, in that 75,4% of all infants, but just 68.8% of AA/B infants, are breastfed at discharge from hospital (2020 data). [8] In specific counties targeted by

the Ohio Equity Institute (OEI, Ohio Department of Health, Bureau of Maternal Child and Family Health) for improvement in birth outcomes, our own Cuyahoga County reports rates of continuing breastfeeding at 8 weeks postpartum of 65.8% among AA/B mothers and 73.9% among all others. [9]

These continuing racial inequities in breastfeeding rates create opportunities for new ways of supporting and promoting breastfeeding for AA/B mothers. Smart phone technology may provide a way to reach and engage AA/B women who otherwise face barriers related to racism in accessing resources for breastfeeding. [10] Approximately 83% of AA/Bs, 76% of those with income < \$30,000 and 95-96% of those ages 18-49 years own a smartphone. [11] There is evidence that mobile health (m-health) applications including telephone support, SMS text messaging and internet-based support can increase rates of postpartum exclusive breastfeeding, however the total number of studies is limited (n=15) with just one focused solely on SMS text messaging. [12] With respect to m-health apps, though, most are solely informational, few are tailored or personalized [13] and very few are designed specifically for AA/B mothers [14]. This gap in m-health products designed with AA/B women's breastfeeding concerns and needs in mind creates another racial inequity; research is needed to overcome this barrier. In prior work we elucidated topics and features that AA/B expectant women intending to or considering breastfeeding would like to see in a phone app [15], and texting/messaging was one specifically endorsed.

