In this research, we follow up on prior work that assessed the feasibility and acceptability and content of a culturally-tuned Breastfeeding-supportive Text Messaging Library intended for AA/B women. That work (TEAM2BF, STUDY20221270) demonstrated that expectant and delivered AA/B women found the text messaging process and content acceptable and helpful. None stopped any or all of the messaging, and approximately 6 messages were revised as recommended by participants. In this current study we aim to obtain preliminary efficacy data by comparing this texting library aimed at promoting breastfeeding to a professionally endorsed national maternal child health texting program, Bright By Text, whose focus is not breastfeeding. By comparing the TEAM2BF texting program to Bright By Text, we can compare whether message content impacts breastfeeding initiation and exclusivity at 2 months. The study design is equitable for participants in that both programs use a similar approach (texting), both are designed to be accessible to minoritized women of low socioeconomic status, and the comparator (Bright By Text) has demonstrated benefits.[16] This study aims to address identified gaps in breastfeeding support for AA/B women that we hope can ultimately reduce racial inequities in breastfeeding rates.

Inclusion and Exclusion Criteria

| | | Inclusion Criteria - mothers |
|--|--|---|
| 1. Expectant women initiating obstetrical care <34 weeks or at any | | Expectant women initiating obstetrical care <34 weeks or at any prenatal visit up |
| | | to 34 weeks gestation |

| 2. | Daily access to a mobile phone with text message capabilities, |
|----|--|
| 3. | 18 years or older (i.e., adult), |
| 4. | Self-identify as African-American/Black, |
| 5. | English speaking, and |
| 6. | Infant feeding plan of "might or will breastfeed". |
| 7. | Receive care at Ahuja Midtown or MAC1200 |

| | Exclusion Criteria |
|--|--------------------------------------|
| 1. | Minors |
| 2. Committed to feeding formula only to their infant | |
| 3. | No mobile phone with text capability |

| | Inclusion Criteria - infants |
|----|--------------------------------|
| 1. | Infant of maternal participant |

| | Exclusion Criteria -infants | |
|----|---------------------------------------|--|
| 1. | 1. Not infant of maternal participant | |

Number of Research Participants

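### The 11% control rate comes from infants not selected on feeding plan, so the rate in eligible women is uncertain; at any rate from 11% to 16%, 36 per arm gives about 6-7% power for a 3-point gain, not 80%

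*Combined protocol and SAP*

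**What the plan says.** The sample-size paragraph of the Data Analysis Plan starts from practice data for 2016-2020, in which "89/808 infants (11%) were exclusively breastfed at 2 months". The infants counted are "full term and late preterm infants not admitted to Neonatal Intensive Care Unit who have an appointment in RPP in first month of life". Nothing is said about the mother's feeding plan or race.

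County WIC data are then said to agree with this estimate: "for the fiscal year 2021 with 594/5188 infants (11.4%) fully breasted". The category is "defined as infants of participating breastfeeding women do not receive formula from the WIC Program".

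The target follows: "An increase from 11% to 14% would be clinically meaningful". With 80% power, alpha 0.05 and a standard deviation capped at 5%, the plan arrives at 36 dyads per group, raised to 40 for 10% attrition. The next paragraph notes that no breastfeeding data are published for Bright By Text participants and names a second meaningful effect, 5 points between arms.

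Under Inclusion and Exclusion Criteria, mothers must self-identify as African-American/Black (AA/B) and have a feeding plan of "might or will breastfeed". Those "Committed to feeding formula only to their infant" are excluded.

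**The concern.** The source of the control rate and the trial population are selected differently. The trial removes the women least likely to breastfeed exclusively, but the planning rate comes from infants not stated to exclude their children. The plan neither adjusts for this nor mentions it.

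The WIC figure does not close the gap. It is tied to a fiscal year rather than to 2 months of age, it covers only formula issued by WIC, and it is not the World Health Organization definition adopted under Outcome Measures. What its denominator of 5,188 represents is not explained. Two figures that both lack the trial's selection cannot validate each other for a selected population.

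At stake is the credibility of the planning statement. The absolute target of 14% has meaning only relative to the right control rate, and the power claim should hold over the rates that eligible women might plausibly show.

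**Working it through.** **The plan's own figure.** 89/808 = 11.0% (Wilson 95% CI 9.0% to 13.4%) and 594/5188 = 11.4%. The 36 per group is reproduced by comparing two means with difference 3 and SD 5, one-sided: 2 × (1.645 + 0.842)² × 25/9 = 34.3, so 35; the t-test version gives 35.04, so 36. Two-sided, the same formula gives 44 (45 with the t-test). 36/0.90 = 40. So 11% enters the 36 only through the 3-point difference.

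**Control rate in eligible women.** Let s be the share of source mothers who might or will breastfeed and q the exclusive rate at 2 months among the rest. The rate in eligible women is (0.11 − (1 − s) × q)/s. The documents do not give s, so the values below are assumptions, some borrowed from initiation and discharge rates in the Background. With q = 0:

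| Assumed s | Basis | 0.11/s |
|---|---|---|
| 90% | assumption | 12.2% |
| 85% | assumption | 12.9% |
| 83.9% | national initiation, all mothers | 13.1% |
| 75.5% | national initiation, AA/B | 14.6% |
| 75.4% | Ohio discharge, all infants | 14.6% |
| 68.8% | Ohio discharge, AA/B | 16.0% |

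The rate equals 14% at s = 0.11/0.14 = 78.6%. With q = 2% it is 13.9% at s = 75.5% and 15.1% at s = 68.8%.

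**Possible downward offset.** If the practice is mixed, its AA/B rate may be below 11%. As an illustration only, apply the Background's national ratio for 6-month exclusive breastfeeding, 19.8/24.9: 0.11 × 19.8/24.9 = 8.7%. Dividing by 0.755 and 0.688 gives 11.6% and 12.7%.

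**What 36 per arm delivers.** Two-proportion normal approximation, two-sided alpha 0.05, difference d = 0.03, mean rate p̄:

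- SE₁ = √[(p₁(1 − p₁) + p₂(1 − p₂))/36] and SE₀ = √[2p̄(1 − p̄)/36]
- power = Φ[(d − 1.96 SE₀)/SE₁] + Φ[(−d − 1.96 SE₀)/SE₁]
- 95% CI half-width = 1.96 SE₁
- n per arm for 80% power = [1.96√(2p̄(1 − p̄)) + 0.842√(p₁(1 − p₁) + p₂(1 − p₂))]²/d²

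| Control rate | n per arm for 80% power | Power at 36 | Half-width at 36 |
|---|---|---|---|
| 11.0% | 1,907 | 6.7% | 15.3 points |
| 12.2% | 2,064 | 6.6% | 15.9 points |
| 14.6% | 2,352 | 6.4% | 17.0 points |
| 16.0% | 2,516 | 6.3% | 17.5 points |

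The power column counts both tails; rejection in favour of Team2BF alone is 5.2% to 5.7%. For the 5-point difference (d = 0.05), power at 36 runs from 9.5% (control 11%) to 8.4% (control 16%).

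**The case against.** A reader might infer that a Team2BF rate of 14% would be taken as success while the control arm does as well or better. The documents do not support that. Hypothesis 2 and the Data Analysis Plan compare the two concurrent randomised arms, and no test against 11% or 14% is planned. If controls reach 15%, the trial will show it.

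A reader might also infer that the control rate is 14.6% to 16.0%. That too goes beyond the documents. The range uses AA/B divisors on a source whose race mix is not stated, whereas the all-mother figures give 13.1% to 14.6%. The Background reports 65.8% of Cuyahoga AA/B mothers still breastfeeding at 8 weeks. If that is a share of all AA/B mothers, a 68.8% starting share would imply 65.8/68.8 = 96% retention, so the local share is probably higher and 16% is an upper end. Women who say they might breastfeed could also outnumber those who start.

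Restricting the practice data to ever-breastfed infants would condition on something that happens after enrolment. It drops eligible women who never start, who remain in the trial's denominator, and so tends to overstate the rate.

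Finally, the 36 does not depend on 11% as such, and correcting the control rate barely moves the power. The larger fault is sizing a yes/no outcome as a mean with SD 5%.

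All of this stands. What remains is that 11% is not justified for the eligible women, the WIC figure does not support it, and the stated 80% power is wrong across the whole range.

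**Conclusion.** The point holds in a limited form. The mismatch between the source of the 11% and the eligibility criteria is in the text, and so is the unsuitable WIC corroboration. The direction and size of the error are not established. About 12% to 16% is plausible if the eligible share is 90% to 69% and almost no other infants are exclusively breastfed at 2 months, with a possible offset for race mix. Whether controls pass 14% depends on whether that share is below 78.6%, which the documents do not tell us. The control arm's breastfeeding messages within Bright By Text (8 up to 4 months, per Study Procedures) could only add to its rate.

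The firm conclusion is about power. From 11% to 16%, 36 per arm gives about 6-7% two-sided power for 3 points and an interval of roughly ±15 to ±18 points. This rests on the normal approximation and 36 analysable dyads per arm. The randomised comparison stays valid; the planning statement needs correcting.

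**What to change.** In the Data Analysis Plan:

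- Remove the WIC figure as corroboration.
- Describe 11% as a figure from infants not selected on feeding plan, and plan over a stated range of control rates, about 11% to 16%.
- If the practice data record prenatal feeding intention and maternal race, re-tabulate by both to narrow the range. Use an ever-breastfed restriction only as an upper bound.
- State the target as a between-arm difference rather than an absolute 14%, and reconcile the 3-point and 5-point figures.
- Replace the 80% power statement with the two-sided power or confidence interval width that 36 per arm gives on a two-proportion basis.

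The cost is rewriting one paragraph, plus a re-tabulation if the fields exist. No extra enrolment or change of procedure is needed. The downside is a less favourable stated figure, which suits the Background's description of the aim as preliminary efficacy data.
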